¹² Death is an outcome, not the SAE itself, so such a name should not appear as a name. If a case of death for an unknown reason is identified, researcher should make every effort to identify its suspected causes. SAE in such cases can be referred to as "Death by unexplained cause" only in cases where the causes of death are not known and cannot be clarified. In case of a fatal outcome due to COVID-19, the information is recorded in the primary medical documentation of the study participant without registration of the SAE.

¹³ The term "Life threatening" in this context means that the volunteer participating in the study was at immediate risk of death during the occurrence of adverse event. This term does not apply to cases where adverse event could hypothetically cause the death of a participant if it were more intense in severity or longer in duration.

¹⁴ Hospitalization for optional or pre-planned treatment of concomitant diseases that the participant had prior to inclusion in the study, the course of which did not worsen during participation in the study, is not considered to SAE, as well as being in a hospital for less than 24 hours or hospitalization for social reasons.

¹⁵ Pregnancy cases in the participants of the clinical study are not subject to registration as AE, except in cases when the child has congenital anomaly or malformation (case is registered as AE).

same time, when closing AE registration form, maximum severity of AE is indicated, which was observed for the entire period of AE persistence as part of the subject's participation in the study.

Recurrent AE – AE, which was completely resolved, for example, during one cycle of therapy, and then reappeared, for example, on the next cycle of therapy, while the participant is in the study. Each recurrent AE is registered separately.

All AE are registered in the primary medical documentation of the participant based on physical examination, survey, and diary records. The following information must be recorded in the primary medical documentation (outpatient card) for each AE:

- severity (mild, moderate, severe);
- nature of adverse event;
- relationship with study drug;
- duration (date of occurrence and end date), preferably with an indication of the time interval (hours) from the moment of administration of the study drug;
- whether adverse event is serious.

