The severity is assessed using the CTCAE scale version 4.03 from 2010. The CCAE scale contains a list of the most frequent AE recorded in clinical study, in tabular format, indicating criteria of various degrees of severity (from 1 to 5, where 5 is death as a result of AE). For AE that are not in the tabulated list, the severity is determined in accordance with the textual description of the degrees of severity.

The terms "serious" and "severe" are not synonymous. The term "severe" is often used to describe the intensity (severity) of a particular event (for example, anemia of severe, moderate or mild severity); however, the event itself may be clinically insignificant (for example, severe headache).

The concept of "severe" is not equivalent to the concept of "serious". The criteria of the latter are the outcome of the event or the measures, which are usually associated with the elimination of life threatening or severe disorders of vital activity. The criterion of seriousness, and not the severity of adverse event, should be guided when determining the need for expedited safety report of LLC "NPP "Pharmaclon" and authorized agencies.

The AE notification form is presented in Appendix 4.

Urgent event:

Urgent events include all serious adverse events.

All SAE detected during the period from the moment of signing the informed consent, even before the application of the first dose of the product under study until the end of the study, are subject to registration. The researcher has the right to provide reports on the development of a disease that has developed at any time after the established mandatory observation period, but it is necessary to provide an appropriate justification for the presence of a causal relationship.

In the event of a serious adverse event, researcher is obliged to:

- provide (if necessary) the study participant with appropriate qualified medical care, including laboratory tests and/or instrumental examinations;

- within 24 hours from the moment when the researcher became aware of the occurrence of adverse event, send the data to LLC NPP Pharmaclon (contact information: [contact]; e-mail: [contact]);
- provide a detailed written report as soon as possible;
- continue monitoring the participant until the full resolution of the SAE.

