Any additional information and supporting documentation (blinded copies of the results of laboratory tests, procedures, pathologist's report or postmortem epicrisis in case of death, etc.) will be provided by the Researcher in additional written messages of LLC NPP Pharmaclon. In case of death of a participant, the Researcher is obliged to provide any additional information at the request of LLC NPP Pharmaclon.

The initial report (completed form of notification of AR) and subsequent detailed and additional reports should identify the subjects of the study by the unique numbers assigned to them, not by the names of the subjects or their addresses and other personal data.

In connection with the occurrence of serious adverse events, the researcher is obliged to notify the ethics committee. The Ethics Committee may, if necessary, discontinue or cancel the study.

The minimum information that should be included in the initial notification of the occurrence of an urgently reported event should contain the identification data of the participant under which he passes in the study, identification data of the person reporting the occurrence of this phenomenon (full name of the chief researcher or authorized employee), characteristics of the event that occurred and its causal relationship with the use of the investigated drug.

Except those cases when the urgently reported event was sufficiently documented in the initial message about its occurrence, the researcher must provide all additional information available to him in subsequent messages about the urgently reported event using the same form, the same ways of its transmission and the time frame as established for the initial message about the urgently reported event. These procedures should continue until AE has been fully documented and reported.

After sending by e-mail the completed SAE notification, researcher must place the originals of the initial and subsequent messages about urgently reported events in investigator file.

Events deemed NOT to require urgent notification include:

- hospitalization for optional or pre-planned treatment of concomitant diseases that the participant had prior to inclusion in the study, the course of which did not worsen during participation in the study;
- hospitalization, death, or life threatening due to the development of complications of ARVI (COVID-19) – however, this information is necessarily recorded and analyzed to assess effectiveness.

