² Death is an outcome, not the SAE itself, so such a name should not appear as a name. If a case of death for an unknown reason is identified, researcher should make every effort to identify its suspected causes. SAE in such cases can be referred to as "Death by unexplained cause" only in cases where the causes of death are not known and cannot be clarified. In case of a fatal outcome due to COVID-19, the information is recorded in the primary medical documentation of the study participant without registration of the SAE.

³ The term "Life threatening" in this context means that the volunteer participating in the study was at immediate risk of death during the occurrence of adverse event. This term does not apply to cases where adverse event could hypothetically cause the death of a participant if it were more intense in severity or longer in duration.

Unexpected adverse event (Unexpected AE) – adverse event, the nature, severity, or outcome of which does not correspond to the information in the current instructions for the medical use of the drug or in Clinical Investigation Brochure for an unapproved drug.

All **unexpected serious adverse events (unexpected SAE)** those recognized by the researcher as related to the drug are classified as **unexpected serious adverse drug reactions (unexpected SAE)**. Serious adverse drug reaction report form is presented in Appendix 3.

Intensity of adverse event

All AE are registered in the primary medical documentation of the participant based on physical examination, survey and diary records. The following information must be recorded in the primary medical documentation (outpatient card) for each AE:

- severity (mild, moderate, severe);
- nature of adverse event;
- relationship with study drug;
- duration (date of occurrence and end date), preferably with an indication of the time interval (hours) from the moment of administration of the study drug;
- whether adverse event is serious.

The severity is assessed using the CTCAE scale version 4.03 from 2010. The CCAE scale contains a list of the most frequent AE recorded in clinical study, in tabular format, indicating criteria of various degrees of severity (from 1 to 5, where 5 is death because of AE). For AE that are not in the tabulated list, the severity is determined in accordance with the textual description of the degrees of severity.

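### Deaths attributed to COVID-19 are kept out of SAE registration, and no safety table shows deaths or ARVI/COVID-19 hospitalisations by arm

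*Protocol*

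**What the plan says.** Both documents define an SAE to include death, threat to life and hospitalisation. Three further rules then apply.

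- **Registration.** Protocol footnote 12, attached to death in the SAE definition, reads: "In case of a fatal outcome due to COVID-19, the information is recorded in the primary medical documentation of the study participant without registration of" an SAE. SAP section 4.2, footnote 2, carries the same rule: "In case of a fatal outcome due to COVID-19, the information is recorded in the primary medical documentation", again with no SAE registered.
- **Urgency.** The protocol's Urgent event section states: "Urgent events include all serious adverse events". It also makes all SAEs from consent to study end subject to registration. The same section then has a list headed "Events deemed NOT to require urgent notification include", which includes "hospitalization, death, or life threatening due to the development of complications of ARVI (COVID-19"). The list adds that "this information is necessarily recorded and analyzed to assess effectiveness".
- **Ethics committee.** "In connection with the occurrence of serious adverse events, the researcher is obliged to notify the ethics committee". No other event is named as a trigger.

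Under Rules for stopping research, the sponsor, the ethics committee or the regulators may stop the study. SAP section 5.6 plans no interim analysis, and neither document describes a data monitoring committee. The study is open-label (SAP section 2.3).

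**The concern.** The outcome that the drug is meant to prevent is also the likeliest source of grave events in this study. Treating infection as an efficacy outcome is reasonable. Removing its fatal cases from the SAE count is a different step, because whether an immunomodulator alters the course of infection in those who catch it is a safety question too.

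Three things are at stake. The SAE comparison in Table 18 would leave out COVID-19 deaths by rule. Whether a death is left out depends on a causal judgement by an investigator who knows the arm. And an unregistered death does not set off the one active notice to the ethics committee that the protocol describes.

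**Working it through.** The point rests on the text, and there is no planned figure to reproduce. The check follows each type of event through the rules and the table shells.

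**1. Death attributed to COVID-19.** It meets the SAE definition, but footnote 12 and SAP section 4.2 bar its registration. Table 18 counts SAEs, so the death cannot appear there. Ethics committee notice depends on an SAE, so none is triggered.

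**2. ARVI or COVID-19 hospitalisation, life-threatening event, or death from an ARVI other than COVID-19.** The exemption list waives urgent notice only, and no rule expressly removes registration. But the same section makes every SAE urgent. Either these events are SAEs and the two statements conflict, or they are not SAEs and the definition is contradicted. The rule that symptoms of acute respiratory infection are not adverse events adds to the doubt. Their place in Table 18 is therefore unclear.

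**3. Other safety tables.** Tables 20, 21 and 23 grade adverse events as mild, moderate or severe. None of the safety tables (17 to 23) has a row for deaths or hospitalisations.

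**4. Efficacy tables.** Tables 13 and 14 give each WHO score by arm, with 3 to 7 for hospitalised states and 8 for death. The condition is scored at every visit. If ARVI is registered, Visit 3 adds a second score for the worst state reached. The SAP does not say which score Table 14 uses. The choice matters, because Visit 3 for a case is held after the quarantine period or hospital discharge. On the current score, a participant who was hospitalised and recovered could be counted as 0 or 1. Table 12 counts complications, which neither document defines. The Secondary Endpoint analysis text in SAP section 5.1 lists four proportions and does not mention the WHO scale.

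**5. Scale, for illustration only.** Inputs: 315 randomised per arm; control incidence of 1 to 5% (protocol, Number of participants); and a severe share of one in five, which the protocol's Introduction reports for the initial outbreak in China. Applying that share to all ARVI cases here is an assumption.

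Expected severe cases = 315 × incidence × severe share. Chance of at least one = 1 − (1 − incidence × severe share)^315.

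| Control incidence | Cases | Severe at 20% | Chance of at least one | Severe at an assumed 1–5% share |
|---|---|---|---|---|
| 1% | 315 × 0.01 = 3.15 | 3.15 × 0.20 = 0.63 | 1 − 0.998^315 = 47% | 0.03 to 0.16 |
| 5% | 315 × 0.05 = 15.75 | 15.75 × 0.20 = 3.15 | 1 − 0.990^315 = 96% | 0.16 to 0.79 |

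These are severe cases, not deaths. The documents give no fatality or hospitalisation rate, so the number of deaths that footnote 12 would remove cannot be projected.

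**The case against.** The strongest reply is that this is a deliberate and consistent choice. ARVI symptoms, ARVI complications and lack of preventive effect are all treated as efficacy information, and many trials spare endpoint events from expedited reporting. That stands as far as the timing of notification goes. It does not justify leaving deaths out of the SAE count when no other by-arm safety display is planned.

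A reader might infer more than the documents support:

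- *That deaths and hospitalisations are counted nowhere.* Not so. Tables 13 and 14 can show them at study end, and a worst-state score is collected. Death cannot resolve before Visit 3.
- *That all grave ARVI/COVID-19 events are removed from the SAE tables.* Only COVID-19 deaths are expressly removed. For the rest only urgent notice is waived.
- *That those able to stop the study could never learn of these events.* The sponsor and ethics committee have direct access to source records, investigators must answer the sponsor's requests about a death, and ARVI cases go on a dedicated form throughout. A separate adverse event guide, cited by the protocol, was not available for this review. These routes are mostly passive, but they exist. The absence of an interim analysis has no bearing on the reporting of single cases.
- *That the rule hides harm from the drug.* Nothing shows this. The protocol says that the drug activates production of acute-phase proteins, but it also calls it an anti-inflammatory cytokine. Under the planning assumptions most cases would fall in the control arm.

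**Conclusion.** The point holds in a limited form and should be corrected. By rule, the SAE count omits deaths attributed to COVID-19, on an attribution made with knowledge of the arm, and those deaths do not trigger ethics committee notice. The SAE status of non-fatal ARVI/COVID-19 hospitalisations and life-threatening events is unresolved, because the protocol's statements on urgent events conflict. The efficacy tables can recover these outcomes at the end, but incompletely unless the maximum score is used.

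The number of events is probably small: from well under one to about three severe cases in a control arm of 315, depending on the assumed incidence and severe share. The primary efficacy analysis is not affected. The conclusion about deaths rests on the wording of the two footnotes alone and not on the illustration. Whether endpoint events should be reported urgently is a design choice that can be argued either way.

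**What to change.** 1. In protocol footnote 12 and SAP section 4.2, footnote 2, delete the closing clause that withholds SAE registration from COVID-19 deaths.
2. Reconcile the two statements in the protocol's Urgent event section, so that any exemption for ARVI/COVID-19 events affects only the timing of notification and not registration or tabulation.
3. Add to the SAP one safety table, by arm, of all-cause deaths, life-threatening events and hospitalisations after randomisation, with a sub-row for those due to ARVI or COVID-19. An all-cause count does not depend on open-label attribution.
4. State in the SAP that Table 14 uses the maximum WHO score for participants with ARVI.

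The cost is some wording, one table, a few extra SAE forms and a slightly less favourable SAE count. No endpoint, sample size or treatment changes.

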4. Open the vial of water for injection by breaking off its upper part.
5. Pour 5 ml of water for injection into glass vial with a dry substance.
6. Remove the dropper cap from the package and fix it on the neck of the bottle.

Due to the need to store the active substance in a full vacuum, the aluminum cap must be hermetic and durable. Slowly remove the aluminum guard of the bottle, avoid cuts. If the cap breaks off during removal, you can remove the rest of the metal cap with scissors.

Take vial with Ingaron with liquid inside with both hands and turn it over 10–15 times.

Put the vial with Ingaron with the liquid inside in the refrigerator and store there for 10 days. For the second course of prevention (after 1 week), use the second vial.

Return the empty ampoules of water for injection together with the used glass vials to the researcher at the next visit.

Administration

Course 1. The drug is applied 3 drops in each nasal passage every other day 30 minutes before breakfast for 10 days (total of 5 instillations). The use of the drug is carried out according to the following regimen:

- Course 1. Day 1 – mark administration time in your diary
- Course 1. Day 3 – mark administration time in your diary
- Course 1. Day 5 – mark administration time in your diary
- Course 1. Day 7 – mark administration time in your diary
- Course 1. Day 9 – mark administration time in your diary

This is 1 preventive cycle. Then a break of 7 days.

Course 2. Drug administration is carried out similarly to Course 1. Preparation of the drug is carried out similarly to the algorithm described earlier. Dosage regimen is the same:

- Course 2. Day 1 – mark administration time in your diary
- Course 2. Day 3 – mark administration time in your diary
- Course 2. Day 5 – mark administration time in your diary
- Course 2. Day 7 – mark administration time in your diary
- Course 2. Day 9 – mark administration time in your diary

If you missed drug administration, mark the day in your diary with a "check mark" and take the next dose the next morning 30 minutes before breakfast and then continue using it every other day. Remember that the finished solution of the drug is stored for no more than 10 days in the refrigerator. Do not use it after the expiration date. For Course 2, use the second bottle, do not use the first bottle, even if the drug is not fully used.

| | |
|---------------------------------|---|
| Course 1 Day 1 | Date ____ ____ ____ ____ ____ ____ day month year |
|---------------------------------|---|

Administration of study drug

Time of administration: | ____ :| ____ |

In case of complaints, symptoms of ARVI, please fill out the table below:

| Start date | End date | Complaints | Therapy (if taken) |
|------------|----------|------------|--------------------|
| | | | |
| | | | |
| | | | |
| | | | |

| | |
|---------------------------------|--|
| Course 1 Day 2 | Date ____ ____ ____ ____ ____ day month year |
|---------------------------------|--|

In case of complaints, symptoms of ARVI, please fill out the table below:

| Start date | End date | Complaints | Therapy (if taken) |
|------------|----------|------------|--------------------|
| | | | |
| | | | |
| | | | |
| | | | |

| | |
|---------------------------------|--|
| Course 1 Day 3 | Date ____ ____ ____ ____ ____ day month year |
|---------------------------------|--|

Time of administration: | ____ :| ____ |

In case of complaints, symptoms of ARVI, please fill out the table below:

| Start date | End date | Complaints | Therapy (if taken) |
|------------|----------|------------|--------------------|
| | | | |
| | | | |
| | | | |
| | | | |

| | |
|---------------------------------|--|
| Course 1 Day 4 | Date ____ ____ ____ ____ ____ day month year |
|---------------------------------|--|

In case of complaints, symptoms of ARVI, please fill out the table below:

| Start date | End date | Complaints | Therapy (if taken) |
|------------|----------|------------|--------------------|
| | | | |
| | | | |
| | | | |
| | | | |

| | |
|---------------------------------|--|
| Course 1 Day 5 | Date ____ ____ ____ ____ ____ day month year |
|---------------------------------|--|

Time of administration: | ____ :| ____ |

In case of complaints, symptoms of ARVI, please fill out the table below:

| Start date | End date | Complaints | Therapy (if taken) |
|------------|----------|------------|--------------------|
| | | | |
| | | | |
| | | | |
| | | | |

| | |
|-----------------|--|
| Course 1 | Date ____ ____ ____ ____ ____ |
|-----------------|--|

| | |
|--------------|----------------|
| Day 6 | day month year |
|--------------|----------------|

In case of complaints, symptoms of ARVI, please fill out the table below:

| Start date | End date | Complaints | Therapy (if taken) |
|------------|----------|------------|--------------------|
| | | | |
| | | | |
| | | | |

| | |
|---------------------------------|--|
| Course 1 Day 7 | Date _____ _____ _____ _____ _____ |
| | day month year |

Time of administration: |_____|:|_____|

In case of complaints, symptoms of ARVI, please fill out the table below:

| Start date | End date | Complaints | Therapy (if taken) |
|------------|----------|------------|--------------------|
| | | | |
| | | | |
| | | | |

| | |
|---------------------------------|--|
| Course 1 Day 8 | Date _____ _____ _____ _____ _____ |
| | day month year |

In case of complaints, symptoms of ARVI, please fill out the table below:

| Start date | End date | Complaints | Therapy (if taken) |
|------------|----------|------------|--------------------|
| | | | |
| | | | |
| | | | |

| | |
|---------------------------------|--|
| Course 1 Day 9 | Date _____ _____ _____ _____ _____ |
| | day month year |

Time of administration: |_____|:|_____|

In case of complaints, symptoms of ARVI, please fill out the table below:

| Start date | End date | Complaints | Therapy (if taken) |
|------------|----------|------------|--------------------|
| | | | |
| | | | |
| | | | |

| | |
|---------------------------------|---|
| Course 2 Day 1 | Date _____ _____ _____ _____ _____ day month year |
|---------------------------------|---|

Administration of study drug

Time of administration: |_____| :|_____|

In case of complaints, symptoms of ARVI, please fill out the table below:

| Start date | End date | Complaints | Therapy (if taken) |
|------------|----------|------------|--------------------|
| | | | |
| | | | |
| | | | |
| | | | |

| | |
|---------------------------------|---|
| Course 2 Day 2 | Date _____ _____ _____ _____ _____ day month year |
|---------------------------------|---|

In case of complaints, symptoms of ARVI, please fill out the table below:

| Start date | End date | Complaints | Therapy (if taken) |
|------------|----------|------------|--------------------|
| | | | |
| | | | |
| | | | |
| | | | |

| | |
|---------------------------------|---|
| Course 2 Day 3 | Date _____ _____ _____ _____ _____ day month year |
|---------------------------------|---|

Time of administration: |_____| :|_____|

In case of complaints, symptoms of ARVI, please fill out the table below:

| Start date | End date | Complaints | Therapy (if taken) |
|------------|----------|------------|--------------------|
| | | | |
| | | | |
| | | | |
| | | | |

| | |
|---------------------------------|---|
| Course 2 Day 4 | Date _____ _____ _____ _____ _____ day month year |
|---------------------------------|---|

In case of complaints, symptoms of ARVI, please fill out the table below:

| Start date | End date | Complaints | Therapy (if taken) |
|------------|----------|------------|--------------------|
| | | | |
| | | | |
| | | | |
| | | | |

| | |
|---------------------------------|---|
| Course 2 Day 5 | Date _____ _____ _____ _____ _____ day month year |
|---------------------------------|---|

Time of administration: |_____| :|_____|

In case of complaints, symptoms of ARVI, please fill out the table below:

| Start date | End date | Complaints | Therapy (if taken) |
|------------|----------|------------|--------------------|
| | | | |
| | | | |
| | | | |
| | | | |

| | |
|---------------------------------|---|
| Course 2 Day 6 | Date _____ _____ _____ _____ _____ day month year |
|---------------------------------|---|

In case of complaints, symptoms of ARVI, please fill out the table below:

| Start date | End date | Complaints | Therapy (if taken) |
|------------|----------|------------|--------------------|
| | | | |
| | | | |
| | | | |

| | |
|---------------------------------|---|
| Course 2 Day 7 | Date _____ _____ _____ _____ _____ day month year |
|---------------------------------|---|

Time of administration: |_____|:|_____|

In case of complaints, symptoms of ARVI, please fill out the table below:

| Start date | End date | Complaints | Therapy (if taken) |
|------------|----------|------------|--------------------|
| | | | |
| | | | |
| | | | |

| | |
|---------------------------------|---|
| Course 2 Day 8 | Date _____ _____ _____ _____ _____ day month year |
|---------------------------------|---|

In case of complaints, symptoms of ARVI, please fill out the table below:

| Start date | End date | Complaints | Therapy (if taken) |
|------------|----------|------------|--------------------|
| | | | |
| | | | |
| | | | |

| | |
|---------------------------------|---|
| Course 2 Day 9 | Date _____ _____ _____ _____ _____ day month year |
|---------------------------------|---|

Time of administration: |_____|:|_____|

In case of complaints, symptoms of ARVI, please fill out the table below:

| Start date | End date | Complaints | Therapy (if taken) |
|------------|----------|------------|--------------------|
| | | | |
| | | | |
| | | | |

Appendix 2

Participant's diary (control group)

LLC "NPP "Pharmaclon"

Medical

Researcher: _____

Contact details: _____

Research Center:

Research participant's diary

Protocol of post-marketing non-interventional study

"A prospective randomized open-label comparative study of the use of the intranasal form of human recombinant interferon gamma for the prevention of acute respiratory viral infections, including diseases caused by coronavirus infection 2019 (COVID-19)"

RAIN-2020

Control Group

Participant screening number: |__|_|__|_|__|_|

Randomization number of the participant: |__|_|__|_|__|_|

Date of signing informed consent: |__|_|__|_|__|_|__|_|__|_|

day month year

The start date for the diary: |__|_|__|_|__|_|__|_|__|_|
day month year

The end date for the diary: |__|_|__|_|__|_|__|_|
day month year

Participant's signature _____

Signature of the medical researcher _____

| Participant _____ (randomization number) | Initial data | Date __ _ __ _ __ _ day month year |
|---|--------------|---|
|---|--------------|---|

| | | |
|---------------------|------------------------------------|----|
| 1. Initials | | |
| 2. Date of birth | | |
| 3. Gender | male / female | |
| 4. Smoking, history | yes (____ pack/day for ____ years) | no |

The observation period is 2 months

If you are taking medications to prevent ARVI, please fill out the table below:

| | |
|---|---------------------------|
| Participant _____ (randomization number) | Observation period |
| Participant _____ (randomization number) | Observation period |

In case of complaints, symptoms of ARVI, please fill out the table below:

¹⁶ Before using the drug, it is necessary to familiarize yourself with the current instructions for medical use to exclude contraindications.

¹⁷ A single dose and the frequency of dosing are indicated

| | | | |
|--|--|--|--|
| | | | |
| | | | |
| | | | |
| | | | |
| | | | |
| | | | |
| | | | |

Appendix 3

Form for reporting unlabeled serious adverse reaction

Reporting of unlabeled serious reaction to a drug being studied in a clinical trial

| | | | | | |
|---|--|--|--|--|--|
| Research protocol No. | | | | | |
| Name of the research protocol | | | | | |
| Name of study drug | | | | | |
| Study phase | | | | | |
| The name of the medical institution in which the SAE was detected | | | | | |

Information about the SAE

| | | | | | |
|--|------------------|--------|-----------|--------------------------|--|
| 1. Initials of the patient | 2. Date of birth | 3. Age | 4. Gender | 5. Start date of the SAE | 6. Mark everything that corresponds to the SAE |
| | | | | | 
 • Death • Hospitalization or its prolongation • Involved persistence of significant disability or incapacity • Life threatening |
| 7. Description of the SAE, including data from laboratory and instrumental studies | | | | | |
| | | | | | |

Information about suspected medicinal product

| | | |
|--|--------------------------|---|
| 8. Suspected medicinal product, including international non-proprietary name or generic name | | 9. Has SAE resolved after drug withdrawal |
| | | 
 • Yes • No • Not applicable |
| 10. Daily dose | 11. Administration route | 12. Did the reaction occur again after repeated use of the drug |
| | | 
 • Yes • No • Not applicable |
| 13. Indications | 14. Dates of treatment | 15. Duration of therapy |
| | from to | |

Concomitant drug therapy and anamnesis

| |
|---|
| 16. Concomitant medications and dates of administration (except those used for the treatment of SAE) |
| |
| 17. Other relevant anamnesis data (for example, diagnoses, allergies, pregnancy with indication of the time of the last menstruation, etc.) |
| |

Other information

| | |
|--|--------------------------------|
| 18. Name and address of the manufacturer | |
| | |
| 19. Case identification number | 20. Date of receipt of the SAE |

| | information by the manufacturer |
|---|--|
| | |
| 21. Source of information about the SAE | |
| • Research • Literature • Healthcare Specialist • Regulatory authorities. • Other | |
| 22. Date of this report | |
| | |
| 23. Type of report | |
| • Initial report | |
| • Follow-up report | |

Appendix 4

ADVERSE DRUG REACTION REPORT FORM MEDICINAL PRODUCT

Primary

Additional information to the message

No. _____ from _____

| Patient data | | | | | | | |
|--|--------------------------------|--|--------------|--|-----------------------|---|------------|
| Patient initials (patient code)* | | | | Gender  M  F Weight kg | | | |
| Age | | Pregnancy  , gestational age weeks | | | | | |
| Allergy  No  Yes | | | | | | | |
| Treatment  outpatient  inpatient  self-treatment | | | | | | | |
| Medications suspected of causing AR | | | | | | | |
| | Name of the drug (trade name)* | Manufacturer | Batch number | Dose, route of administration | Therapy starting date | Therapy end date | Indication |
| 1 | | | | | | | |
| 2 | | | | | | | |
| 3 | | | | | | | |
| Adverse reaction | | | | | | AR initial date | |
| Description of the reaction* (specify all details, including laboratory data) | | | | | | Criteria for AR severity:  Death  Life threatening - Hospitalization or its extension  Disability  Congenital anomalies  Clinically significant event  Not applicable | |
| Date of AR resolving | | | | | | | |
| Interventions | | | | | | | |
|  Without treatment  Withdrawal of suspected medicinal product  Drug dose tapering  Non-drug therapy (including surgical intervention)  Drug therapy | | | | | | | |
| Outcome | | | | | | | |
|  Recovery without complications  Recovering or resolving  Condition without changes  Recovery with complications (specify) _____  Death  Unknown  Not applicable | | | | | | | |

| Was drug withdrawal accompanied by AR resolving? | |  No  Yes  No drug withdrawal  Not applicable | | | | | |
|---|-------------------------------|--|--------------|-------------------------------|-----------------------|---|------------|
| Has medicinal product been prescribed repeatedly? | |  No  Yes | | Result | |  Not applicable | |
| Other medications taken during the last 3 months, including drugs taken by the patient independently (at his own request) | | | | | | | |
| | Name of the drug (trade name) | Manufacturer | Batch number | Dose, route of administration | Therapy starting date | Therapy end date | Indication |
| 1 | | | | | | | |
| 2 | | | | | | | |
| 3 | | | | | | | |
| 4 | | | | | | | |

| | | | | | | | | |
|--|--|--|--|--|--|--|--|--|
| 5 | | | | | | | | |
| Data of the reporting person | | | | | | | | |
